5 STUDY TREATMENTS

5.1 Treatment Groups

After completion of the screening period and qualifying Screening Visit, patients who meet all eligibility criteria (except those criteria scheduled to be assessed after the Screening Visit) will enter a 2-week run-in period. During this time, all patients will be given open-label placebo.

At the Day 1 Visit (scheduled within 4 ± 2 days after the end of the run-in period [Visit 3]), eligible patients will be randomized by Interactive Response Technology (IRT) in a 1:1:1 ratio to the following treatment groups:

- KBP-5074 0.25 mg QD orally,
- KBP-5074 0.5 mg QD orally, or
- Placebo QD orally

The duration of the double-blind treatment period will be 84 days. Patients will remain on their stable antihypertensive medication (ie, no change in antihypertensive medication) throughout the entire study (including both the run-in and treatment periods). The dose of diuretic may be adjusted based on developing or resolved edema, weight gain or loss, or pulmonary congestion.

5.2 Rationale for Dosing

As outlined in Section 1, based on data from preclinical and clinical efficacy, safety, PK, and relative bioavailability studies, KBP BioSciences has determined that 0.25 mg and 0.5 mg QD are the appropriate dosage for a planned Phase 2b study using the KBP-5074 tablet formulation. Clinical data were derived from 102 study subjects who participated in 4 Phase 1 studies, which included healthy normal subjects and patients with mild, moderate, and severe CKD, including patients receiving HD. Data show that study drug exposure, as expressed by several PK measures (AUC, C_{max}), is similar for healthy subjects and patients with mild-to-moderate CKD. Exposure is increased, however, in patients with severe CKD (up to around 60% higher AUC and C_{max}). Analysis of safety data from the Phase 1 studies suggests a possible correlation between increased exposure (AUC > 3000 ng*h/ml) and risk of hyperkalemia. The fragility of patients with severe CKD implies that sensitivity to drug and/or increases in free drug levels could substantially potentiate wanted and unwanted pharmaceutical effects in this population. These effects may be amplified with the use of the tablet formulation of KBP-5074, which has an approximately 18% higher C_{max} than the capsule formulation.

5.3 Randomization and Blinding

This is a randomized, double-blind, placebo-controlled study. Patients will be randomized to one of the 3 treatment groups listed in Section 5.1. Randomization will be stratified based on the following values at baseline:

- eGFR: \geq 30 versus < 30 mL/min/1.73 m², and
- SBP: $\geq 160 \text{ versus} < 160 \text{ mmHg}$.

Individual treatment assignments will be blinded to the Sponsor, Investigator, study personnel, and patients throughout the course of the study. All individuals directly involved in the conduct of the study, including data management personnel, will remain blinded to treatment assignments.

5.4 Breaking the Blind

At all times, study personnel will attempt to safeguard the integrity of the blinding in order to minimize bias in the conduct of the study. Breaking of the blind should not occur except in the case of a medical emergency and should occur after discussion with the Medical Monitor. In such a case, the Investigator may access this information by contacting the Sponsor or its designee. If the blind is broken for an individual patient, the blinding should be preserved for the remainder of the patients throughout the duration of the study. In such a case, study personnel may be notified of that individual patient's treatment assignment without jeopardizing study blinding for the overall study.

If the blind is broken for a patient, the patient may or may not be asked to withdraw from the study. This decision will be based on Investigator consultation with the Medical Monitor. All patients will be asked to continue study visits to the end of the study whether or not they remain on study drug. If a patient must temporarily discontinue study drug, they may or may not be able to restart study drug. This decision will be based on Investigator consultation with the Medical Monitor.

5.5 Drug Supplies

5.5.1 Formulation and Packaging

KBP-5074 tablets are supplied as 0.25 mg and 0.5 mg strengths for this study. The weight of the 0.25 mg and 0.5 mg tablets are 109.5 mg and 111.0 mg, respectively.

For the 0.25 mg strength, each unit of KBP-5074 drug product contains 0.23% KBP-5074 drug substance, 36.53% of microcrystalline cellulose PH101 (FMC, United States Pharmacopeia [USP]/National Formulary [NF]) as filler, 54.79% of lactose monohydrate (MEGGLE, USP/NF) as filler, 3.2% of croscarmellose sodium (FMC, USP/NF) as disintegrant agent, 2.28% of hydroxypropyl methyl cellulose E50 (DOW, USP/NF) as binder, 1.14% of sodium lauryl sulfate (BASF, USP/NF) as solubilizer, 0.91% magnesium stearate (GREVEN, USP/NF) as lubricant, and 0.91% silicon dioxide (GRACE, USP/NF) as flow agent.

For the 0.5 mg strength, each unit of KBP-5074 drug product contains 0.45% KBP-5074 drug substance, 36.04 % of microcrystalline cellulose PH101 (FMC, USP/NF) as filler, 54.05% of lactose monohydrate (MEGGLE, USP/NF) as filler, 3.15% of croscarmellose sodium (FMC, USP/NF) as disintegrant agent, 2.25% of hydroxypropyl methyl cellulose E50 (DOW, USP/NF) as binder, 2.25% of sodium lauryl sulfate (BASF, USP/NF) as solubilizer, 0.90% magnesium stearate (GREVEN, USP/NF) as lubricant, and 0.90% silicon dioxide (GRACE, USP/NF) as flow agent.

For the placebo, each unit of placebo contains 36.20% of microcrystalline cellulose PH101 (FMC, USP/NF) as filler, 54.30% of lactose monohydrate (MEGGLE, USP/NF) as filler, 3.17% of croscarmellose sodium (FMC, USP/NF) as disintegrant agent, 2.26% of hydroxypropyl methyl cellulose E50 (DOW, USP/NF) as binder, 2.26% of sodium lauryl sulfate (BASF, USP/NF) as solubilizer, 0.90% magnesium stearate (GREVEN, USP/NF) as lubricant, and 0.90% silicon dioxide (GRACE, USP/NF) as flow agent.

KBP-5074 tablets will be packaged in polypropylene bottles and closed by low-density polyethylene bottle caps with drying agent. Each polypropylene bottle will contain 35 tablets of drug product.

Each bottle will be labeled in English, the language appropriate to the investigational site participating in the study, and according to country-specific requirements. Label text will be approved according to the Sponsor's agreed procedures.

For all study drugs, a system of numbering in accordance with all requirements of Good Manufacturing Practice will be used, ensuring that each dose of study drug can be traced back to the respective bulk ware of the ingredients. A complete record of batch numbers and expiry dates of all study drug, as well as the labels, will be maintained in the Sponsor's study file.

5.5.2 Study Drug Preparation and Dispensing

Study drug will be dispensed as indicated on the Schedule of Procedures (Appendix A). At each visit where study drug is dispensed, the Investigator or designee will provide patients with sufficient study drug until the next scheduled dispensing visit.

5.5.3 Study Drug Administration

Patients will take 1 tablet of either KBP-5074 0.25 mg, KBP-5074 0.5 mg, or placebo orally QD.

5.5.4 Treatment Compliance

If a patient's compliance with open-label placebo and/or current antihypertensive medications is < 80% or > 120% during the run-in period, the patient will not be eligible for the study, and no further visits will be performed.

Patient compliance with study drug will be assessed by clinical site personnel via tablet counts of returned study drug and by questioning the patient, if necessary, at every post-randomization visit. A patient who is not compliant (has taken < 80% or > 120% of study drug) will be counseled at each visit on the importance of taking study drug as instructed.

5.5.5 Storage and Accountability

Study drug must be stored in a secure area according to local regulations so that only the Investigator and other designated personnel have access to the study drug. The study drug should be stored at 15°C to 25°C and protected from light and moisture.

The study drugs will be shipped to the investigational site.

All unused and/or partially used study drug, except retention samples, must be returned to Worldwide Clinical Trials (Worldwide), if not authorized by the Sponsor to be destroyed at the site, prior to or upon completion or termination of the study.

All study drugs returned to Worldwide must be accompanied by the appropriate documentation and be clearly identified. Returned supplies should be in their original containers. Empty bottles may be returned to Worldwide; however, it is the Investigator's responsibility to arrange disposal of all empty containers. The return of unused study drug should be arranged by the assigned site monitor.

5.6 Prior and/or Concomitant Medications and/or Procedures

5.6.1 Excluded Medications and/or Procedures

Use of the following medications is not permitted during the study:

- MRAs other than KBP-5074;
- Potassium binders used for treatment of hyperkalemia from 3 months prior to Screening until the end of study assessments, including but not limited to calcium polystyrene (eg, sorbisterit, calcium resonium), sodium polystyrene (eg, kayexalate, anti-kalium sodium), patiromer (eg, Veltassa), and sodium zirconium cyclosilicate (eg, Lokelma);
- Potassium-sparing diuretics (eg, amiloride, triamterene) within 3 months prior to Screening until the end of study assessments;
- Potassium supplements (unless clinically indicated on an emergent basis to treat hypokalemia until serum potassium values are within the normal range [see Section 8.12]);
- Hemodialysis/peritoneal dialysis;
- Any nutrients known to modulate CYP3A activity (based on the KBP-5074 metabolic pathway) or any strong or moderate inhibitors or inducers of CYP3A4, starting from 14 days prior to the first dose of study drug at Day 1 until the end of study assessments, including, but not limited to the following: inhibitors, such as ketoconazole, miconazole, itraconazole, fluconazole, atazanavir, erythromycin, clarithromycin, ranitidine, and cimetidine, and inducers, such as rifampicin, rifabutin, systemic glucocorticoids (inhaled and topical permitted), carbamazepine, phenytoin, phenobarbital, and St. John's wort; and
- Any other medications (prescription drugs, herbal products, vitamins, minerals, and over-the-counter medications) that potentially increase serum potassium levels and/or cause toxicity to the kidney, including chronic or daily use of nonsteroidal anti-inflammatory drugs. These medications should be taken only if the Investigator considers these medically necessary. It is recommended that serum potassium levels and eGFR values should be closely monitored when patients take these medications.

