At Screening and the end of the placebo run-in period (Visit 3), patients must have uncontrolled hypertension (Grade 1 to 2 systolic hypertension – ESC/ESH), defined as resting trough-cuff seated SBP \geq 140 and \leq 179 mmHg, based on the mean of at least 2 current consecutive blood pressure readings in the clinic and a serum potassium \leq 4.8 mmol/L at Screening and the end of the placebo run-in period (Visit 3), and a mean (Visit 1 and Visit 3) eGFR \geq 15 and \leq 44 mL/min/1.73 m².

In all cases, dose and frequency of concurrent antihypertensive medications are expected to be maintained without dose adjustment for 30 days prior to randomization in order to ensure that blood pressure is stable. In general, patients should not add or adjust dose and/or types of the antihypertensive medications they are receiving during the screening period and throughout the duration of the study (unless they develop symptomatic hypotension). The dose of diuretic may be adjusted based on developing or resolved edema, weight gain or loss, or pulmonary congestion.

Patients will be advised to maintain their normal diet and avoid unhealthy levels of alcohol use or potassium-rich foods/drinks during the study period. No potassium supplements are permitted, unless clinically indicated to treat hypokalemia on an emergent basis until serum potassium values

are within the normal range. The use of potassium-sparing diuretics is not permitted within 3 months prior to Screening until the end of study assessments. Intermitted or chronic use of potassium-binding drugs is not permitted for 3 months prior to Screening until the end of study assessments.

After completion of the screening period and the qualifying Screening Visit, patients who meet all eligibility criteria (except those criteria scheduled to be assessed after the Screening Visit), will enter the 2-week, open-label (placebo) run-in period. At the end of the run-in period (Visit 3), patients will be reassessed for eligibility, including persistence of uncontrolled hypertension and compliance with open-label placebo received during the run-in period and current antihypertensive medication. If a patient's compliance is < 80% or > 120%, the patient will not be eligible for the study, and no further visits will be performed.

[figure not shown]

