4.2 Exclusion Criteria

Patients who meet any of the following criteria will be excluded from participation in the study:

- 1. Resting trough-cuff seated SBP ≥ 180 or < 140 mmHg, based on the mean of at least 2 current consecutive clinic blood pressure readings at Screening and the end of the placebo run-in period (Visit 3);
- 2. Serum potassium > 4.8 mmol/L;
- 3. Compliance with medications (including both open-label placebo and current antihypertensive medications) < 80% or > 120% during the run-in period (assessed at Visit 3);
- 4. Currently on an MRA (eg, spironolactone or eplerenone) other than KBP-5074, or received any MRAs during the last 3 months prior to Screening, or currently on any potassium supplements;
- 5. Chronic or intermittent use of a potassium binder for the treatment of hyperkalemia from 3 months prior to Screening until the end of study assessments, including but not limited to calcium polystyrene sulfonates (eg, sorbisterit, calcium resonium), sodium polystyrene sulfonates (eg, kayexalate, anti-kalium sodium), and patiromer (eg, Veltassa[™]) and sodium zirconium cyclosilicate (eg, Lokelma[™]);
- 6. Have routinely or chronically used or required potassium-sparing diuretics (eg, amiloride, triamterene) within 3 months prior to Screening until the end of study assessments;
- 7. History of known/suspected contraindications, allergy, or intolerance to MRAs (eg, spironolactone, eplerenone) or has a known hypersensitivity to KBP-5074, other MRAs, or related compounds;
- 8. Clinically significant hyperkalemia while on an angiotensin converting enzyme inhibitor, angiotensin receptor blocker, direct renin inhibitor, and/or MRA, requiring down-titration or discontinuation of above medication, or hospitalization for hyperkalemia within 3 months prior to Screening, or hyperkalemia > 5.6 mmol/L during the 2 weeks prior to Screening;
- 9. History/diagnosis of renal artery stenosis or history/diagnosis of renovascular hypertension;
- 10. Currently receiving HD, or peritoneal dialysis within 3 months prior to Screening, and those patients with an episode of acute kidney injury within 3 months of Screening;

- 11. History of a renal transplant, or impending renal transplant;

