4.3 Withdrawal Criteria

Participation of a patient in this clinical study may be discontinued for any of the following reasons:

- The patient withdraws consent or requests discontinuation from the study for any reason;
- Significant protocol violation, including major protocol violations, such as taking prohibited medication or inability to comply with protocol procedure;

- Any clinically significant adverse event, severe laboratory abnormality, intercurrent illness, or other medical condition that indicates to the Investigator that continued participation is not in the best interest of the patient, including:
 - Hypertensive Emergency;
 - Hyperkalemia defined in Table 1; or
 - Sustained increase in serum creatinine defined as an increase > 50% in serum creatinine from baseline and confirmed by a repeated test (see Section 8.13);
- Pregnancy;
- Termination of the study by the Sponsor or regulatory authority; or
- Lost to follow-up.

If a patient withdraws prematurely from the study due to the above criteria or any other reason, study staff should make every effort to complete the full panel of assessments scheduled for the Early Termination Visit (see Section 6.6). The reason for patient withdrawal must be documented in the electronic Case Report Form (eCRF).

In the case of patients lost to follow-up, attempts to contact the patient must be made and documented in the patient's medical records.

Withdrawn patients will not be replaced.

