8.12 Safety Surveillance and Management of Serum Potassium Levels

Serum potassium levels of study patients will be monitored systematically throughout the study. In addition to the clinical laboratory tests pre-defined in the Schedule of Procedures (Appendix A), unscheduled assessments of serum potassium levels are recommended under certain situations (eg, vomiting and/or diarrhea for ≥ 1 day) that may impact patients' serum electrolyte levels or fluid balance.

In patients with serum potassium above the normal laboratory reference range (serum potassium levels $\geq 5.0 \text{ mmol/L}$), it is advised that the Investigator should reinforce dietary restriction for management of elevated potassium and consider local guideline recommendations. Table 1 below summarizes the laboratory testing for assessment of serum potassium levels $\geq 5.0 \text{ mmol/L}$ and guidelines for management of study drug, which includes continuation thereof, holding of study drug, and/or discontinuation of study drug. If serum potassium levels are < 5.0 mmol/L, no action is indicated. A serum potassium level of $\geq 5.6 \text{ mmol/L}$ requires a hold of study drug and appropriate retesting and intervention as described in Table 1. A potassium level of $\geq 6.0 \text{ mmol/L}$ necessitates immediate and permanent discontinuation of study drug.

Because of potential issues anticipated from routine sample handling and extended transportation time to the central laboratory, pseudohyperkalemia secondary to hemolysis may occur in centrally analyzed laboratory samples. For this reason, during treatment with study drug, all serum potassium assessments, including retests, will be performed at both local and central laboratories.

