Following notification of a serum K ⁺ alert value ¹		Contact patient and schedule repeat serum K ⁺ within 24-72 hours after laboratory notification.	Contact patient and schedule repeat serum K ⁺ within 24-48 hours after laboratory notification.	Contact patient and schedule repeat serum K ⁺ within 24 hours after laboratory notification.
Management	Continue study drug.	Continue study drug pending retest results.	Hold study drug pending retest results.	Permanently discontinue study drug.
Treatment If first serum K ⁺ retest is < 5.3 mmol/L	Reinforce low K ⁺ diet.	Reinforce low- K ⁺ diet; manage HK per local SOC (no K ⁺ binders). Continue study drug.	Reinforce low- K ⁺ diet; manage HK per local SOC (no K ⁺ binders). Resume study drug.	Reinforce low- K ⁺ diet; manage HK per local SOC (may use K ⁺ binders)
Management following first serum K ⁺ retest		If retest serum K ⁺ is ≥ 5.3 to 5.5 mmol/L: 1. Hold study drug, 2. Consider higher dose of diuretic, 3. Schedule second serum K ⁺ retest within 1 week. If retest serum K ⁺ > 5.5 mmol/L, permanently discontinue study drug.	 If retest serum K⁺ is ≥ 5.3 to 5.5 mmol/L: 1. Continue to hold study drug, 2. Consider higher dose of diuretic, 3. Schedule second serum K⁺ retest within 1 week. If retest serum K⁺> 5.5 mmol/L, permanently discontinue study drug. 	Note: Following discontinuance of study drug continue study visits and safety monitoring.
Management following second serum K ⁺ retest		If serum K ⁺ on retest is < 5.3 mmol/L, continue study drug. If serum K ⁺ on retest is ≥ 5.3 mmol/L, permanently discontinue study drug.	If serum K ⁺ is < 5.3 mmol/L, resume study drug. If serum K ⁺ on retest is ≥ 5.3 mmol/L, permanently discontinue study drug.	
Adverse Event Reporting		Report as AE of Special Interest	Report as AE of Special Interest	Report as AE as Special Interest

In the absence of hemolysis, the more conservative value from the central or local laboratories should be used to guide management and treatment Study sites should make repeated attempts to contact patients with high K⁺ or HK to ensure compliance with K⁺ safety monitoring and required retests.

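### Section 5.6.1 bars potassium binders for hyperkalemia until the end of study assessments, while Table 1 permits them at 6.0 mmol/L or more in patients who stay in follow-up

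*Combined protocol and SAP*

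**What the plan says.** **The ban.** Section 5.6.1 lists what may not be used during the study. One entry is "Potassium binders used for treatment of hyperkalemia from 3 months prior to Screening until the end of study assessments", followed by product examples. It carries no exception and no cross-reference. The potassium-supplement entry in the same list has both: an allowance for emergent use and a pointer to Section 8.12.

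Exclusion criterion 5 names "Chronic or intermittent use of a potassium binder for the treatment of hyperkalemia from 3 months prior to Screening until the end of study assessments". Section 3.1, speaking of intermittent or chronic use, says "potassium-binding drugs is not permitted for 3 months prior to Screening until the end of study assessments". The synopsis says the same.

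**The permission.** Table 1 (Section 8.12) treats binders by potassium band. For 5.3 to 5.5 and for 5.6 to 5.9 mmol/L it says "manage HK per local SOC (no K ⁺ binders"). For 6.0 mmol/L or more it says "manage HK per local SOC (may use K ⁺ binders"). In Section 8.12 a level in that top band "necessitates immediate and permanent discontinuation of study drug", and the Table 1 column adds that visits and safety monitoring go on afterwards. The text below the table adds that a patient who needs chronic or intermittent binder treatment comes off study drug permanently.

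**What follows from a breach.** Section 4.3 gives reasons for which participation may be discontinued, among them "Significant protocol violation, including major protocol violations, such as taking prohibited medication". It separately lists hyperkalemia as defined in Table 1. Section 5.4 asks all patients to attend to the end of the study, on or off study drug.

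**The concern.** Both instructions are operative and both concern the most severe potassium level in the protocol. A site that works from Section 5.6.1 has a written reason not to use a treatment that Table 1 permits. A site that works from Table 1 may find the same treatment logged as prohibited medication, and Section 4.3 then allows it to withdraw a patient whom Table 1 and Section 5.4 want followed.

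At stake are consistent safety management across about 90 sites and, if a patient is withdrawn, the potassium, safety and Day 84 SBP measurements that would otherwise have been collected.

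**Working it through.** No arithmetic decides this point. The passages, side by side:

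| Place | Binder use covered | Applies until | Exception |
|---|---|---|---|
| 5.6.1 | Use to treat hyperkalemia, no qualifier | End of study assessments | None |
| Exclusion 5 | Chronic or intermittent use | End of study assessments | None |
| 3.1 and synopsis | Chronic or intermittent use | End of study assessments | None |
| Table 1, 6.0 mmol/L or more | Use per local standard of care | Not limited; visits continue | Permits use |
| 8.12, text below Table 1 | Chronic or intermittent need | Not limited | Consequence is stopping study drug |

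1. **Does the ban still reach the patient Table 1 describes?** Yes. In the top band study drug stops, but the patient remains in study visits. The ban ends with study assessments, and the End of Study visit is Day 112 (Section 6.5), not the last dose. The patient is inside the ban when Table 1 allows the binder.

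2. **Is there an exception elsewhere?** Section 5.6.2 refers to Section 8.12 for monitoring and managing raised potassium, but only in general terms, and it does not modify 5.6.1. No section says which text prevails.

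3. **Which passages conflict with which?** Section 5.6.1 has no qualifier, so it conflicts with Table 1 outright. Exclusion 5, Section 3.1 and the synopsis cover chronic or intermittent use. They conflict with the text below Table 1, which foresees exactly that use in a patient who has stopped drug but not left the study. Against a single acute use under Table 1 their conflict is only arguable.

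4. **What does the protocol attach to a breach?** Section 4.3 makes prohibited medication an example of a major violation that may end participation. Section 9.1 leaves the list of major deviations to be fixed before unblinding, so the classification is possible, not certain.

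5. **Which analyses could be touched?**
   - Severe hyperkalemia is defined by potassium of 6.0 mmol/L or more (Section 8), so the event has been recorded before Table 1 permits a binder.
   - The Per-Protocol Population requires completion of 84 days of treatment (Section 9.1). A patient stopped earlier is already outside it; only an event near Day 84 or in follow-up could be reclassified.
   - The patient stays in the ITT analysis of SBP, where Section 9.2.2.1 uses the last double-blind value if Day 84 is missing. An observed Day 84 value could be lost.
   - Later scheduled potassium and safety data are lost if the patient is withdrawn.

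6. **How many patients?** The documents give no rate. As an assumed range only, 2% to 5% of an 80-patient arm reaching 6.0 mmol/L would be 80 × 0.02 = 1.6 to 80 × 0.05 = 4 patients. That is an upper bound for data loss under the assumption, because only those given a binder and then withdrawn on that account lose data.

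**The case against.** The best defence is that Section 8.12 is specific and coherent. It refuses binders in the two bands where study drug may continue or resume, and allows them only where drug is stopped for good. Its text on chronic or intermittent need fits that pattern. Section 5.6.2 sends the reader there, and Section 8.12 also tells the investigator to treat as appropriate whether or not drug is stopped. A sensible site would probably follow Table 1. This stands as a comment on likely practice: the barrier to treatment is weak. It does not change the formal status of the binder under 5.6.1.

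A second objection is that binder use adds little to the risk of withdrawal, because Section 4.3 already lists Table 1 hyperkalemia as a reason in its own right. This also stands. It exposes a related mismatch: 4.3 lets that patient's participation end, while Table 1 says visits continue.

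A reader might infer that every binder passage flatly forbids what Table 1 allows. The documents do not support that: only 5.6.1 is unqualified, and exclusion 5 is written as an entry criterion. A reader might also infer that following Table 1 is automatically a major violation. Section 4.3 is permissive and the list of major deviations is still open, so that does not follow either.

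**Conclusion.** The inconsistency is real and stands in the current text. Section 5.6.1 and Table 1 give opposite answers on binders at 6.0 mmol/L or more, and permanent discontinuation of study drug does not reconcile them. The conclusion rests on reading the end of study assessments as the end of the patient's visits, which is the natural sense.

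The size is modest. The number of patients is likely small, but no rate is given, so this is a judgement. Severe-hyperkalemia incidence and the Per-Protocol set are essentially unaffected. The residual risk is uneven safety management and possible loss of later potassium, safety and Day 84 SBP follow-up where a site withdraws the patient.

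It is tempting to go further and claim a dose-related loss of primary data. Section 1 reports hyperkalemia in the high-dose groups of an earlier study, and Section 5.2 mentions a possible link with exposure, so imbalance between arms is plausible. But the documents give no rate by arm and no indication of how often binder use would lead to withdrawal. A material bias cannot be asserted from them.

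**What to change.** - Reconcile Section 5.6.1, Section 3.1, the synopsis, exclusion 5 and Table 1 with its accompanying text in 8.12, so that all state one rule for binders after study drug is permanently stopped. Add a cross-reference from 5.6.1 to Table 1. Which clinical rule applies is for the sponsor to choose.
- State in Section 4.3 whether treatment given under Table 1 counts as a prohibited-medication violation.
- Reconcile the Table 1 hyperkalemia reason in Section 4.3 with the instruction in Table 1 to continue visits, making clear whether stopping study drug or leaving the study is meant.

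The cost is a few sentences and cross-references in a protocol amendment. No new data, visits or procedures are needed.
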